### 15.6.5. Pharmacokinetic

General
Dose Level

 
Summaries by dose level and used tablet strength will be based on an actual dose associated with a container number. (See Section 15.6.2). Tablet strength is defined as follows: 
 
Actual dose = 1 mg → 1 mg tablet strength
 
Actual dose = 2 mg → 2 mg tablet strength
 
Actual dose = 4 mg → 4 mg tablet strength
 
Actual dose = 6 mg → 6 mg tablet strength
 
Actual dose = 8 mg → 4 mg tablet strength
 
Actual dose = 12 mg → 6 mg tablet strength
 
Actual dose = 18 mg → 6 mg tablet strength
 
Actual dose = 24 mg → 6 mg tablet strength
 
 
 
Dose level which is actually provided to subjects will be derived from an actual dose of the visit (including unscheduled visit) which meets the following: 
 
Treatment Start Date ≤ Date of last dose taken prior to PK sampling ≤ Treatment Stop Date
 
 
 

Others

 
Dose normalized PK parameters will be derived from [PK parameters / actual dose (mg)].
 
In aggregated analyses, data collected in Week 12 and Week 24 will be aggregated.
 
For the PK parameters calculation, the concentration at 0 hr will be set to 0 and assign zero to NQ values.
 
Individual's PK parameters calculated less than 4-time point concentrations or any time deviated (beyond ± 30 min of scheduled timepoints) concentrations will be omitted from summaries and figures, but presented in a listing.
 

### 15.6.6. Exploratory Endpoint

Iron Endpoints
Subjects Who Used IV and Oral Iron

 
Number of subjects who used IV and/or oral iron will be summarized
 
Subjects who used IV and oral iron will be defined as follows:
 

- Subjects with on-therapy IV and/or oral iron medication collected in a specific eCRF form (CONMEDS-IRON).
- Subjects who used Riona (GSK drug code=00752601) will also be regarded as baseline iron use subjects in a subgroup analysis and also counted for oral iron use in this summary.
- Regarding oral iron use, the number of subjects who used Riona and other than Riona will also be counted respectively.

**IV Iron Dose by Quarter**

- Records of on-therapy iron medication will be used for the following calculations
- Monthly average IV iron during the treatment period = Total IV iron dose (mg) during the treatment period / (duration in the treatment period (days) / 30.4375 days)
- Monthly average IV iron by quarter = Total IV iron dose during each quarter (mg) / (duration in a quarter (days) / 30.4375 days).
- Total IV iron dose during each quarter (mg) will be carried with the following formula using each record. Duration will be derived from iron medication start/stop date:
  - Total IV iron dose during each quarter (mg) = (iron dose1\*frequency1\*duration1) + ... + (iron dosen\*frequencyn\*durationn)
  - Duration (days) = (stop date1 - start date1 + 1) + ... + (stop daten - start daten + 1)
 Frequency is defined as follows:
  - If subject receives iron dose with once daily → frequency = 1
  - If subject receives iron dose with BID → frequency = 2
  - If subject receives iron dose with TID → frequency = 3
  - If subject receives iron dose with QID → frequency = 4
  - If subject receives iron dose with every x week → frequency = 1/(7\*x) If subject receives iron dose with every x week → frequency = 1/(7\*x)
  - If subject receives iron dose with x times per week → frequency = x/7
  - If subject receives iron dose with x times per month → frequency = 1/(30.4375\*x)

Total IV iron during the treatment period will be carried in the same manner.

- Quarters will be defined as follows:

	Start Date	End Date
Treatment period	Randomization Date	Treatment Stop Date
Quarter 1	Randomization Date	Treatment Start Date at Week 12 - 1 day
Quarter 2	Treatment Start Date at Week 12	Treatment Start Date at Week 24 - 1 day
Quarter 3	Treatment Start Date at Week 24	Treatment Start Date at Week 40 - 1 day
Quarter 4 	Treatment Start Date at Week 40	Treatment Stop Date

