#### Blood Products and Blood Supportive Care Products (On-Therapy)

The number and percentage of subjects who use blood products and/or blood supportive care products will be provided by treatment group and total. The details for the use will also be summarized.

- **Dialysis**

Baseline Mode of Dialysis

The number and percentage of subjects with each baseline mode of dialysis (i.e. haemodialysis, haemofiltration, or haemodiafiltration) will be provided by treatment group and total. The period of time on dialysis (years) will be summarized using mean, standard deviation, median, minimum, and maximum.

Baseline Mode of Vascular Access

The number and percentage of subjects with each baseline mode of vascular access will be provided by treatment group and total. Previous vascular access will be summarized in the same manner.

- **Exposure and Treatment Compliance**

Exposure to Study Treatment

Full details of exposure definition are presented in Section [15.6.2](#).

Time on study treatment (days), subject daily dose (for daprodustat) or weekly dose (for darbepoetin alfa), and cumulative dose will be summarized using the number of subjects exposed, mean, standard deviation, median, minimum, and maximum. Time on study treatment will be categorized in different time periods (< 3 months, 3 months to 6 months, >6 months to 12 months, >12 months; 1 month = 30.4375 days) and the number and percentage of subjects exposed will be displayed for each category.

Treatment Compliance

Full details of treatment compliance definition are presented in Section [15.6.2](#).

The number and percentage of subjects within each category will be summarized by treatment and total for up to Week 4, Week 40 to 52, and overall. The categories will be classified into under compliant, compliant, over compliant. Note that this is a double-dummy study but a summary will be made for the active treatment and a listing will contain both active and placebo compliance.

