### Demographics and Baseline Characteristics

standardized to obtain a continuous single unit prior ESA dose in terms of epoetin IV (IU/week). The standardization will be carried with the following formula based on literature review:

- For subjects taking epoetin IV
  - Standardized mean prior ESA dose (IU/week) = epoetin IV dose (IU/week)
- For subjects taking epoetin SC
  - Standardized mean prior ESA dose (IU/week) = (161/113)\*epoetin SC dose(IU/week): [Besarab. 2002]
- For subjects taking darbepoetin alfa IV or SC
  - Standardized mean prior ESA dose (IU/week) = 250\*darbepoetin alfa dose (µg/week)
- For subjects taking epoetin beta pegol IV or SC
  - Standardized mean prior ESA dose (IU/week) = 208\*epoetin beta pegol dose (µg/week)
- Prior ESA dose will be calculated using a weighted mean:
  - Mean prior ESA dose (µg/week or IU/week) =  $([dose\_w]_1 * [duration]_1 + \dots + [dose\_w]_n * [duration]_n) / ([duration]_1 + \dots + [duration]_n)$   
 where
    - $[Dose\_w]_n = [dose]_n * [frequency]_n$
    - $[Duration]_n = [Prior\ ESA\ start\ date]_{n+1} - [prior\ ESA\ start\ date]_n^*$   
 or  
 $[Randomization\ date] - [prior\ ESA\ start\ date]_n^*$   
 when  $n^{th}$  record is the last prior ESA dose

\*Using "[end date] – [start date] + 1" may be inappropriate because the start date may be identical with the end date in case the dose frequency is once daily or twice daily, etc.

Note: Frequency is defined as follows:

If subject receives prior ESA x times per week → frequency = x

If subject receives prior ESA every x weeks → frequency = 1/x

If subject receives prior ESA x times per month → frequency = x \* 7 / 30.4375

If subject receives prior ESA x times per day → frequency = x \* 7/duration

once daily (QD) = 1 time per day, twice daily (BID) = 2 times per day, etc...

- Prior ESA dose during the period of 12 weeks prior to randomization will be used for calculation.
- To obtain this, some records may be converted for calculation because some dosing records may include both before and after the period or may not include the period.
  - If a start date of dosing is before 12 weeks prior to randomization (i.e., study day < -84), the start date will be replaced to the date of study day = -84 for the calculation.
  - This conversion makes the records before 12 weeks prior to randomization ignorable because the records will lose their information and weighting of duration before the period.

Demographics and Baseline Characteristics						

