Illustration of Standardized Mean Prior ESA calculation (ex: epoetin IV)						
Record#	Visit	Start Date	Dose (IU)	Frequency. [unit]	Duration (days)	Dose_w (IU / week)
1	Screening	06Feb2017	750	Once daily	2	$750 * 7/2 = 2625$
2	Screening	08Feb2017	750	Once daily	2	$750 * 7/2 = 2625$
3	Screening	10Feb2017	1500	Once daily	3	$1500 * 7/3 = 3500$
4	Screening	13Feb2017	750	3 [times/week]	9	$750 * 3 = 2250$
-	Day 1	22Feb2017 [Randomization Date]				Weighted mean (IU/week) = 2578.1
Erythropoietin Resistance Index (ERI) at Baseline						

 
Calculated as standardized mean prior ESA dose (IU/week) divided by dry weight (kg) at screening visit and then divided by the achieved Day 1 Hgb (g/dL).
 
						

Exposure									
Blinded Dose Level									

 
Blinded dose level of each visit will be linked with prescribed dose according to the protocol:
 
									
Dose level	0	1	2	3	4	5	6	7	8
Treatment	Prescribed Dose								
Daprodustat / Placebo	0 mg	1 mg	2 mg	4 mg	6 mg	8 mg	12 mg	18 mg	24 mg
Darbeoetin Alfa / Placebo	0 µg	10 µg	15 µg	20 µg	30 µg	40 µg	60 µg	NA	NA

 
In darbeoetin alfa / placebo treatment, prescribed dose will be associated with exposure records. Two records of exposure within a certain visit form have a certain blinded dose level.
 
									
Prescribed Dose and Actual Dose									

 
Prescribed dose will be derived from blinded dose level captured in eCRF.
 
Actual dose will be derived from container number(s) captured in eCRF. Note that unscheduled (additional) bottles will not be taken into account. In principle, actual dose will be the same as prescribed dose except for a case in which inconsistency between a prescribed dose and actual bottle(s) occurs. If such an inconsistency occurs, it may not be possible to determine what dose was actually taken. In these cases, the actual dose may be changed from the prescribed dose to a more plausible value based on the available information (e.g., IRT data).
 
									
Extent of Exposure of Daprodustat									

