
 
Subjects who were randomized but did not report a treatment start date will be categorized as having zero days of exposure.
 
Time on study treatment will be calculated based on the following formula: Time on study treatment (days) = [Study Treatment Stop date] – [Study Treatment Start date] + 1 day The time on study treatment does not exclude dose interruptions.
 
									

Exposure

 
• Cumulative dose will be based on the formula using actual dose: Cumulative Dose = Sum of ([Exposure Duration] x [Actual Dose]) at Each Visit where Exposure duration = [Treatment Stop date] – [Treatment Start date] +1 day
 
• Subject daily dose (= Cumulative Dose / Time on study treatment) is calculated for each subject using actual dose and the summary statistics are calculated based on the subject average daily dose.
 
• Distribution of the dose level Dose level will be classified into 9 categories; 0 mg (i.e. treatment interruption), 1 mg, 2 mg, 4 mg, 6 mg, 8 mg, 12 mg, 18 mg, 24 mg according to actual dose.
 

Extent of Exposure of Darbepoetin Alfa

 
• Subjects who were randomized but did not report a treatment start date will be categorized as having zero days of exposure.
 
• Time on study treatment will be calculated based on the following formula: Time on study treatment (days) = [Study Treatment Stop date] – [Study Treatment Start date] + 1 day The time on study treatment does not exclude dose interruptions.
 
• Cumulative dose will be based on the formula using actual dose: Cumulative Dose = Sum of Actual Dose at Each Visit
 
• Subject weekly dose (= Cumulative Dose / Time on study treatment) is calculated for each subject using actual dose and the summary statistics are calculated based on the subject average weekly dose.
 
• Distribution of the dose level Dose will be classified into 7 categories; 0 µg (i.e. treatment interruption), 10 µg, 15 µg, 20 µg, 30 µg, 40 µg, 60 µg according to actual dose.
 

Treatment Compliance of Daprodustat

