
 
• Treatment compliance of darbepoetin alfa will be based on dosing records (weekly doses are captured) and categorized as Under Compliant, Compliant, and Over Compliant, and will be defined as follows:             
 
○ Calculated compliance < 80% → Under Compliant
 
○ Calculated compliance ≥ 80% and ≤ 120% → Compliant
 
○ Calculated compliance > 120% → Over Compliant
 
 
 
• Calculated compliance will just be carried to derive compliance category, not provided for any displays. It will be carried using the following formula:             
 
○ Calculated compliance (%) = [(Total # of dosing records with container number) / (Total # of planned dosing)] * 100
 
             where              Total # of planned dosing = [Time on study treatment (days)] / 7              where Time on study treatment (days) = Treatment Stop Date – Treatment Start date + 1           
 
 
When a container number is available in a visit, subjects will receive an injection in the visit (i.e., dosing records may be available even when subjects don't receive injections).
 
 
• For compliance up to Week 4, following formulae will be used:             
 
Total # of actual dosing up to Week 4 = Sum of (Number of dosing records with container number before Week 4 visit)
 
Total # of planned dosing up to Week 4 = [Time on study treatment (days) up to Week 4] / 7
 
• Time on study treatment (days) up to Week 4                = [Week 4 Dosing Date] – [Treatment Start date] + 1 day                If Week 4 dosing date is missing (i.e., withdrawal before Week 4), treatment stop date will be used instead.
 
 
 
• For compliance during the primary efficacy evaluation period, following formulae will be used:             
 
Total # of actual dosing during the EP = Sum of (Number of dosing records with container number on and after Week 40 visit).
 
Total # of planned dosing during the EP = [Time on study treatment (days) during the EP] / 7
 
• Time on study treatment (days) during the EP                = [Treatment Stop Date] – [Week 40 Dosing Date] + 1 day                If Week 40 dosing date is missing (i.e., withdrawal before Week 40), the compliance will not be calculated.
 
 
 

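### Two SAP derivation formulas are wrong as written: the monthly IV iron frequency is inverted (low by x² per record), and the darbepoetin weekly dose is divided by days (7-fold low)

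*SAP*

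**What the plan says.** **IV iron (SAP 15.6.6, IV Iron Dose by Quarter).** Total dose in a period is the sum over records of dose × frequency × duration, with duration counted in days. The total is then scaled to a month of 30.4375 days. Frequency is defined by a list of rules. The weekly one is "If subject receives iron dose with x times per week → frequency = x/7". The monthly one begins "If subject receives iron dose with x times per month → frequency = 1/(30.4375" and closes with a multiplication by x inside the bracket, so it is 1/(30.4375·x).

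The prior ESA derivation in SAP 15.6.2 has a rule for the same monthly category, expressed per week: "If subject receives prior ESA x times per month → frequency = x \* 7 / 30.4375".

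**Darbepoetin exposure (SAP 15.6.2, Extent of Exposure of Darbepoetin Alfa).** The unit of time is days: "Time on study treatment (days) = [Study Treatment Stop date" and so on, stop minus start plus one. The dose summary is "Subject weekly dose (= Cumulative Dose / Time on study treatment) is calculated for each subject using actual dose". SAP 6.2 sends it to the exposure display: "subject daily dose (for daprodustat) or weekly dose (for darbepoetin alfa), and cumulative dose will be summarized". The compliance rule for the same drug uses the same time variable but converts it to weeks: "Total # of planned dosing = [Time on study treatment (days)] / 7".

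**The concern.** In each case the printed formula does not give the quantity its label names, and the SAP's own neighbouring rules show this.

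- **Iron.** Because duration is in days, frequency must be a daily rate. The daily, every-x-weeks and times-per-week rules all are. The monthly rule has the shape of an every-x-months rule.
- **Darbepoetin.** The same quotient, cumulative dose over days, is called a daily dose for daprodustat and a weekly dose for darbepoetin. It cannot be both.

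Appendix 6 is the specification programmers work from, and nothing elsewhere in the SAP overrides these lines. The August 2018 revision history lists changes to the exposure and iron endpoint parts of 15.6, but none of them touches these two formulas.

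What is at stake is descriptive. IV iron dose over the treatment period and over Weeks 40 to 52 (Quarter 4) is a protocol exploratory endpoint with darbepoetin as control, so unequal use of the monthly code between arms would distort that comparison. The darbepoetin weekly dose in Table 1.26 would be wrong for every subject and would contradict the dose-by-visit displays (Tables 2.25 and 2.27) in the same report.

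**Working it through.** The SAP gives no worked number for either formula. Its one worked dose-frequency example, the prior ESA weighted mean in 15.6.2, does reproduce: (2625×2 + 2625×2 + 3500×3 + 2250×9)/16 = 2578.125, printed as 2578.1 IU/week.

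**IV iron**

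Inputs: the frequency rules in SAP 15.6.6 and the 30.4375-day month in SAP 15.6.1. The 40 mg dose is an assumption for illustration.

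1. Daily rate for x administrations a month: x/30.4375. The prior ESA rule agrees: (x × 7/30.4375) per week ÷ 7 = x/30.4375 per day.
2. Correct over written: (x/30.4375) ÷ (1/(30.4375·x)) = x².
3. Monthly average for 40 mg per administration:

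| x per month | Written (mg) | Correct (mg) | Factor low |
|---|---|---|---|
| 1 | 40 | 40 | 1 |
| 2 | 20 | 80 | 4 |
| 3 | 13.3 | 120 | 9 |
| 4 | 10 | 160 | 16 |

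4. Comparison with a near-equivalent regimen: once a week gives 1/7 = 0.143 per day. Four times a month gives 0.0082 per day as written and 0.131 when corrected.
5. Effect on a group mean. Let p be the share of true IV iron dose that comes from monthly-coded records, all with the same x. The understatement is p(1 − 1/x²). The documents do not give p, so a range is shown:

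| p | x = 2 | x = 4 |
|---|---|---|
| 0% | 0% | 0% |
| 10% | 7.5% | 9.4% |
| 25% | 18.8% | 23.4% |
| 50% | 37.5% | 46.9% |

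**Darbepoetin weekly dose**

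Inputs: the SAP 15.6.2 definitions. Assumed: constant dosing, 52 weekly injections, and 365 days from Day 1 to an on-schedule Week 52 visit. Both weekly records in each visit form are summed, in line with "Two records of exposure within a certain visit form have a certain blinded dose level".

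| Weekly dose | Written: 52 × dose/365 | Corrected: 52 × dose/(365/7) |
|---|---|---|
| 10 µg | 1.42 | 9.97 |
| 20 µg | 2.85 | 19.95 |
| 60 µg | 8.55 | 59.84 |

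The factor is exactly 7 whatever the duration. For a subject who withdraws after 10 injections of 20 µg (70 days), the written rule gives 200/70 = 2.86 and the corrected rule 20.0. With the compliance rule's divisor, 52/(365/7) = 99.7%, which confirms that days ÷ 7 is the right scale. Protocol Table 8 has 10 µg as its lowest dose level, so even constant 60 µg dosing would be reported below it.

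**The case against.** **The iron label, not the formula, may be the slip.** The expression 1/(30.4375·x) mirrors the every-x-weeks rule in the same list, which is printed twice, so the list was loosely edited. If the eCRF code means every x months, the values would be right and only the label wrong. The eCRF codes are not in the documents, so this cannot be excluded. It does not rescue the rule as printed, because label and formula disagree under either reading.

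**The iron effect may be nil.** Nothing shows that any IV iron record is coded monthly with x above 1, and the shares used above are hypothetical. This stands: the per-record error is certain for the label as printed, but its effect on the tables is unknown.

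**The darbepoetin intent is plain and the error would be seen.** The quantity is called weekly, SAP 15.6.1 sets a week at 7 days, and a year at 60 µg printing as 8.55 would look absurd. The revision history also mentions team review of dry-run outputs. This makes an undetected error less likely, but it does not make the formula correct. The iron error has less protection, because it is diluted among other records: if half a quarter is coded weekly and half as four times a month at the same dose, the subject's total is low by a factor of about 1.8, which could pass unnoticed.

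**The list of affected tables cannot be fully confirmed.** The display shells are separate documents, and Listing 15 might also show the derived weekly dose. This is fair, and it would add a listing rather than another analysis.

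**Conclusion.** The concern holds. Followed literally, the darbepoetin rule understates every subject's weekly dose exactly 7-fold in Table 1.26. The iron rule, applied to the label as printed, understates each monthly-coded IV iron record by x² (4-fold at x = 2, 16-fold at x = 4, none at x = 1) in Tables 2.30 and 2.32. The effect on the iron group means depends on the unstated share of such records. For x = 2 it runs from 0% to 37.5% low as that share goes from 0% to 50%.

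The reach is limited. The primary and principal secondary analyses, the counts of iron users, the iron parameter models, the compliance categories, the cumulative dose, the daprodustat daily dose and the dose-by-visit tables do not use either formula. These are errors in descriptive derivations that should be corrected before programming is final.

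**What to change.** - **SAP 15.6.6:** for x administrations per month, set frequency to x/30.4375. Check the eCRF frequency codes. If an every-x-months code exists, keep 1/(30.4375·x) for that code only and label it so.
- **SAP 15.6.2:** define the darbepoetin subject weekly dose as cumulative dose ÷ (time on study treatment in days ÷ 7), matching the compliance rule. State that the cumulative dose sums both weekly exposure records in each visit form.
- **Programs:** check the derivation code for Tables 1.26, 2.30 and 2.32, and Listing 15 if it shows the weekly dose.

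The cost is two formula lines, one clarifying sentence and the matching code. Data collection and the confirmatory analyses do not change.

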
 
Based on literature review the distribution of hepcidin is skewed and requires a log-transformation. Calculation of statistics on log-transformed data are described in Section 5.2
 
	

Iron Use Subgroup

 
Subjects who used Riona will also be regarded as baseline iron use subjects in a subgroup analysis.
 
The baseline iron use will be defined as follows: 
 
A subject takes a pre-therapy iron medication and/or a pre-therapy medication of the GSK drug code = 00752601 (FERRIC CITRATE; Riona).
 
 
 

**15.6.7. Patient Reported Outcome**

[figure not shown]
The original version of instructions and questionnaire items for the study are written in Japanese. In displays, the items will be translated into English version (can be found at <http://www.qualitymetric.com> for SF-36v2, EuroQol products for EQ-5D-5L).

SF-36v2
Overview of Scoring Algorithm

 
Scores will be calculated by Optum PRO CoRE. Refer to “User’s Manual for the SF-36v2 Health Survey Third Edition, 2011” for further details.
 
Three sets of summary scores will be calculated based on responses to each item on the SF-36: 
 
Physical Component Summary (PCS) score
 
Mental Component Summary (MCS) score
 
 
 

**SF-36v2**

- Domain scores based on the following eight domains
  - Physical Functioning
  - Role-Physical (i.e., role limitations due to physical health)
  - Bodily Pain
  - General Health
  - Vitality
  - Social Functioning
  - Role-Emotional (i.e., role limitations due to mental/emotional health)
  - Mental Health

The scoring process is summarized in the following figure (Refer to Figure 5.1 in [User's Manual](#) for the SF-36v2 Health Survey Third Edition, 2011).

Before submitting an SF-36v2 response set for scoring, the following points will be ensured.

- SF-36v2 Acute is being used for this study.
- Missing values will be estimated using the *Maximum Data Recovery Mode*.
- 2009 U.S. general population will be set for scoring.

